8. INFORMED CONSENT, DATA PROTECTION, TRIAL RECORDS

The trial will be carried out in compliance with the protocol, the principles laid down in the Declaration of Helsinki, in accordance with the ICH Harmonised Tripartite Guideline for Good Clinical Practice (GCP) and relevant BI SOPs and the Japanese GCP regulations (Ministry of Health and Welfare Ordinance No. 28, March 27, 1997).

Standard medical care (prophylactic, diagnostic and therapeutic procedures) remain the responsibility of the subject's treating physician.

The investigator should inform the sponsor immediately of any urgent safety measures taken to protect the trial subjects against any immediate hazard, and also of any serious breaches of the protocol or of ICH GCP and the Japanese GCP regulations (Ministry of Health and Welfare Ordinance No. 28, March 27, 1997).

8.1 STUDY APPROVAL, SUBJECT INFORMATION, AND INFORMED CONSENT

This trial will be initiated only after all required legal documentation has been reviewed and approved by the respective IRB / Independent Ethics Committee (IEC) and competent authority (CA) according to national and international regulations. The same applies for the implementation of changes introduced by amendments.

Prior to a subject's participation in the trial, written informed consent must be obtained from each subject (or the subject's legally accepted representative) according to ICH GCP and to the regulatory and legal requirements of the participating country. Each signature must be personally dated by each signatory and the informed consent and any additional subject information form are to be retained by the investigator as part of the trial records. A copy of the signed and dated written informed consent and any additional subject information must be given to each subject or the subject's legally accepted representative.

The subject must be informed that his/her personal trial-related data will be used by Boehringer Ingelheim in accordance with the local data protection law. The level of disclosure must also be explained to the subject.

The subject must be informed that his or her medical records may be examined by authorised monitors (Clinical Monitor Local/Clinical Research Associate) or Clinical Quality Assurance auditors appointed by Boehringer Ingelheim, by appropriate IRB/IEC members, and by inspectors from regulatory authorities.

8.2 DATA QUALITY ASSURANCE

A quality assurance audit/inspection of this trial may be conducted by the sponsor or sponsor's designees, by IRBs/IECs, or by regulatory authorities. The quality assurance auditor will have access to all medical records, the investigator's trial-related files and correspondence, and the informed consent documentation of this clinical trial.

The data management procedures to ensure the quality of the data are described in detail in the trial data management and analysis plan (TDMAP) available in the trial master file.

8.3 RECORDS

CRFs for individual subjects will be provided by the sponsor. For drug accountability, refer to [Section 4.1.8](#).

8.3.1 Source documents

Source documents provide evidence for the existence of the subject and substantiate the integrity of the data collected. Source documents are filed at the investigator's site.

All data reported in the CRFs must be consistent with the source data or the discrepancies must be explained.

The investigator may need to request previous medical records or transfer records, depending on the trial.

8.3.2 Direct access to source data and documents

The investigator/institution will permit trial-related monitoring, audits, IRB/IEC review and regulatory inspection, providing direct access to all related source data/documents. CRFs and all source documents, including progress notes (if applicable) and copies of laboratory and medical test results must be available at all times for review by the sponsor's clinical trial monitor, auditor and inspection by health authorities (e.g. FDA). The Clinical Research Associate/on site monitor and auditor may review all CRFs, and written informed consents. The accuracy of the data will be verified by reviewing the documents described in Section 8.3.1.

8.3.3 Storage period of records

Trial site:

The trial site must retain the source and essential documents (including ISF) according to the national or local requirements (whatever is longer) valid at the time of the end of the trial.

Sponsor:

The sponsor must retain the essential documents according to the sponsor's SOPs.

8.4 EXPEDITED REPORTING OF ADVERSE EVENTS

BI is responsible to fulfil their legal regulatory reporting obligation and in accordance to the requirements defined in this CTP.

10. APPENDICES

Not applicable.

2. LIST OF ABBREVIATIONS

Term	Definition / description
AE	Adverse Event
CTP	Clinical Trial Protocol
ICH	International Conference On Harmonisation
MedDRA	Medical Dictionary For Regulatory Activities
PK	Pharmacokinetics
PV	Protocol Violation
RPM	Report Planning Meeting
SD	Standard Deviation
TSAP	Trial Statistical Analysis Plan

3. INTRODUCTION

As per ICH E9 (1), the purpose of this document is to provide a more technical and detailed elaboration of the principal features of the analysis described in the protocol, and to include detailed procedures for executing the statistical analysis of the primary and secondary variables and other data.

This TSAP assumes familiarity with the Clinical Trial Protocol (CTP), including Protocol Amendments. In particular, the TSAP is based on the planned analysis specification as written in CTP Section 7 “Statistical Methods and Determination of Sample Size”. Therefore, TSAP readers may consult the CTP for more background information on the study, e.g., on study objectives, study design and population, treatments, definition of measurements and variables, planning of sample size, randomization.

SAS® Version 9.4 will be used for all analyses.

4. CHANGES IN THE PLANNED ANALYSIS OF THE STUDY

There are no changes in the planned analysis of the study.

[figure not shown]
5. ENDPOINTS(S)

5.1 PRIMARY ENDPOINT(S)

No efficacy endpoints will be evaluated in this trial. Primary endpoints are defined in CTP (see Section 5.5.1.1).

5.2 SECONDARY ENDPOINT(S)

Secondary endpoints are defined in CTP (see Section 5.5.1.2).

5.4 OTHER VARIABLE(S)

Safety of the investigational drugs will be assessed based on:

- Adverse events (including clinically relevant findings from the physical examination)
- Safety laboratory tests
- 12-lead ECG
- Vital signs (blood pressure, pulse rate)

Demographic data:

- Gender (male)
- Ethnicity (Not Hispanic/Latino)

- Race (Asian)
- Age [years]=integer[(date of informed consent – date of birth)/365.25]
- Height [cm]
- Weight [kg]
- Body mass index (BMI) [kg/m²] = weight [kg] at screening / (height [m] at screening)²
- Smoking status (Never smoked, Ex-smoker, Currently smokes)
- Alcohol status (Does not drink any alcohol; Drinks alcohol, but to an extent that would not interfere with participation in trial; Drinks alcohol to an extent that could interfere with participation in trial)

6. GENERAL ANALYSIS DEFINITIONS

6.1 TREATMENT(S)

6.1.1 TREATMENT REGIMENS / STUDY INTERVALS

There will be 10 phases in this trial:

screening, the first reference treatment (Ref 1), the second reference treatment (Ref 2), the first tablet treatment (Test 1), the second tablet treatment (Test 2), Washout 1 - 3, Post-treatment and post-study.

The treatment regimens/intervals in which a subject can lie during the course of the trial are defined as Table 6.1.1: 1.

Table 6.1.1: 1 Treatment regimens/Intervals.

Label	Sort order	Start date (CRF)	Start time (CRF/derived)
Screening	00	Date of informed consent	0:00
Ref 1	01	Date of the first Ref administration	Time of the first Ref administration
Ref 2	02	Date of the second Ref administration	Time of the second Ref administration
Test 1	03	Date of the first Test administration	Time of the first Test administration
Test 2	04	Date of the second Test administration	Time of the second Test administration
Washout 1	05	Date of last administration of Period 1	Time of last administration in Period 1 + 1 minute
Washout 2	06	Date of last administration of Period 2	Time of last administration in Period 2 + 1 minute
Washout 3	07	Date of last administration of Period 3	Time of last administration in Period 3 + 1 minute
Post-treatment	09	Date of last administration	Time of last administration + 1 minute
Post-study	99	Date of EOT + 1	0:00

KEY: Ref (Reference treatment): DE commercial capsule formulation; Test (Tablet Formulation): investigational formulation

6.2 IMPORTANT PROTOCOL VIOLATIONS

Data discrepancies and deviations from the CTP will be identified for all subjects in the database (i.e., treated subjects and subjects with serious AE (SAE) which the investigator considered related to the screening procedure). Consistency check listings (for identification of violations of time windows) and a list of protocol deviations (e.g. deviations in drug administration, in blood sampling times, etc.) will be provided to be discussed at the report planning meeting (RPM). At this meeting, it will be decided whether a discrepant data value can

be used in analyses or whether it must be corrected in the clinical database.

Each protocol deviation must be assessed to determine whether it is an important protocol violation (PV). For definition of important PVs, and for the process of identification of these, refer to the Boehringer Ingelheim reference document 'Protocol Violation Handling Definitions' (7).

If any important PVs are identified, they are to be summarised into categories and will be captured in the RPM minutes via accompanying Excel spreadsheet (8) [001-MCS-50-413_RD-02]. The following table contains the categories which are considered to be important PVs in this trial. If the data show other important PVs, this table will be supplemented accordingly by the time of the RPM.

If substantial numbers of PVs are reported at the RPM, a decision about summarising the PVs in a tabular format will be made. Otherwise, only a PV listing will be provided.

Table 6.2: 1 Important protocol violations

Category / Code	Description	Requirements/Comment	Excluded from
A	Entrance criteria not met		
A1.1	Inclusion criteria violated	Automatically detectable	None
A2	Exclusion criteria violated	Automatically detectable	PKS
B	Informed consent		
B1	Informed consent not available/not done	Informed consent date is missing or informed consent is not given. Automatically detectable	All
B2	Informed consent too late	Informed consent date was after screening visit Automatically detectable	None
C	Trial medication and randomisation		
C1	Non-compliance with trial medication	No trial drug administration. Automatically detectable	TS and PKS
C2	Incorrect trial medication taken	e.g. trial medication was swapped, Manually detectable	None
C3	Improper intake of trial medication	Manually detectable	PKS
C4	Improper washout between treatments	Washout period has to be more than 3 days. Automatically detectable	PKS
D	Concomitant medication		
D1	Administration of any drugs and/or intake of any foods which might influence the results of PK.	For example; Administration of any drugs before or during the trial Violation of restricted lifestyle Manually detectable.	PKS
E	Missing data		
E1	Certain violations of procedures used to measure primary or secondary data	Violations of procedures which may lead to invalid measurements with respect to primary or secondary PK endpoints. Manually detectable	PKS
F	Incorrect timing		
F1	Certain violations of time schedule used to measure primary or	PK sample taken too early/too late Manually detectable	PKS

Category / Code	Description	Requirements/Comment	Excluded from
	secondary data		

6.3 SUBJECT SETS ANALYSED

- **Randomised set (RS):**
This subject set includes all randomised subjects, whether treated or not.
- **Treated set (TS):**
This subject set includes all subjects from the RS who were dispensed study medication and were documented to have taken at least one dose of investigational treatment.
- **Pharmacokinetic set (PKS):**
This subject set includes all subjects from the TS who provide at least one observation for at least one primary endpoint that was not excluded according to the description above. Thus, a subject will be included in the PKS, even if he contributes only one primary endpoint value for one period to the statistical assessment.

The discussion of all exceptional cases and problems and the decisions on the allocation of subjects to populations will be made at latest at the RPM.

The following table summarizes which subject sets will be used for the different analyses.

Table 6.3: 1 Subject sets analysed

Class of endpoint	RS	TS	PKS
Disposition, exposure	X		
Important PVs	X		
Primary endpoints			X
Secondary and further endpoints			X
Safety endpoints		X	
Demographic/baseline endpoints		X	X

6.5 POOLING OF CENTRES

Pooling centres is not planned in the study, since the study is conducted in one site.

6.6 HANDLING OF MISSING DATA AND OUTLIERS

Data of screened subjects, who discontinued from the trial due to screening failures prior to administration of any trial medication, will not be included in the CTR except for those with SAE which the investigator considered related to the screening procedures. The safety data of treated subjects who were withdrawn from the trial prematurely will be reported as far as available. All withdrawals will be documented and the reason for withdrawal recorded.

Handling of missing data is described in section 7.4 of the CTP. Additionally, handling missing data is described as follows:

Missing or incomplete AE dates are imputed according to BI standards (see “Handling of missing and incomplete AE dates”) (3).

Missing data and outliers of PK data are handled according to (2).

6.7 BASELINE, TIME WINDOWS AND CALCULATED VISITS

The baseline values of laboratory data and value of vital sign for safety analysis will be defined as the last values before drug administration of period 1.

In this trial, calculated visits will not be planned.

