2. Breath alcohol test and safety laboratory. Safety laboratory to be taken and to be medically evaluated within 24 hours prior to administration of trial drug. Samples for safety laboratory will be collected after the subjects have fasted for at least 10 hours except for Visit 1. Breath alcohol test will be performed at screening and within 24 hours prior to each treatment period, and may be repeated at any time during the trial.
3. The time is approximate; the procedure can be acceptable to be performed and completed within 3 h prior to drug administration.
4. If several actions are indicated at the same time point, the intake of meals will be the last action.
5. End of trial examination includes physical examination, body weight, vital signs, ECG, safety laboratory, recording of AEs and concomitant therapies.
6. AEs and concomitant therapies will be recorded throughout the trial, but will be specifically asked for at the time points indicated in the [Flow Chart](#) above.
7. In case of premature discontinuation, 5-14 days after the last drug administration

TABLE OF CONTENTS

TITLE PAGE	1
CLINICAL TRIAL PROTOCOL SYNOPSIS	2
FLOW CHART	4
TABLE OF CONTENTS	5
ABBREVIATIONS	8
1. INTRODUCTION.....	10
1.1 MEDICAL BACKGROUND	10
1.2 DRUG PROFILE	10
2. RATIONALE, OBJECTIVES, AND BENEFIT - RISK ASSESSMENT	14
2.1 RATIONALE FOR PERFORMING THE TRIAL	14
2.2 TRIAL OBJECTIVES.....	14
2.3 BENEFIT - RISK ASSESSMENT	14
3. DESCRIPTION OF DESIGN AND TRIAL POPULATION.....	16
3.1 OVERALL TRIAL DESIGN AND PLAN	16
3.1.1 Administrative structure of the trial.....	16
3.2 DISCUSSION OF TRIAL DESIGN, INCLUDING THE CHOICE OF CONTROL GROUP(S).....	17
3.3 SELECTION OF TRIAL POPULATION	18
3.3.1 Main diagnosis for study entry	18
3.3.2 Inclusion criteria	18
3.3.3 Exclusion criteria	18
3.3.4 Removal of subjects from therapy or assessments.....	20
3.3.4.1 Removal of individual subjects.....	20
3.3.4.2 Discontinuation of the trial by the sponsor	20
3.3.5 Replacement of subjects	21
4. TREATMENTS.....	22
4.1 TREATMENTS TO BE ADMINISTERED.....	22
4.1.1 Identity of BI investigational product and comparator products	22
4.1.2 Method of assigning subjects to treatment groups	23
4.1.3 Selection of doses in the trial.....	23
4.1.4 Drug assignment and administration of doses for each subject	23
4.1.5 Blinding and procedures for unblinding	24
4.1.6 Packaging, labelling, and re-supply	24
4.1.7 Storage conditions.....	24
4.1.8 Drug accountability	25

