2.3 BENEFIT - RISK ASSESSMENT

Participation in this trial is without any (therapeutic) benefit for healthy subjects. Their participation in the trial, however, is of major importance to the development of tablet formulation of DE. The subjects are exposed to the risks of the trial procedures and the risks related to the exposure to the trial medication.

Procedure-related risks

The use of an indwelling venous catheter for the purpose of blood sampling may be accompanied by mild bruising and also, in rare cases, by transient inflammation of the wall of the vein. In addition, in rare cases a nerve might be injured while inserting the venous catheter, potentially resulting in paresthesia, reduced sensibility, and/or pain for an indefinite period. The same risks apply to veinipuncture for blood sampling.

The total volume of blood withdrawn during the entire trial per subject will be around 285 mL. No health-related risk to healthy subjects is expected from this blood withdrawal.

Drug-related risks and safety measures

[figure not shown]
The most significant potential risk associated with DE is a minor bleeding tendency at doses 600 mg and higher per day during steady state in Caucasian healthy volunteers [U00-1856]. For Japanese healthy volunteers, bleeding event was observed after treatment with a single dose of 300 mg. For details of adverse events in Japanese subjects included in phase I trials, see the [Section 1.2](#).

In Japan, DE has market authorisation with the dose regimen of 150 mg b.i.d. (reduction to 110 mg b.i.d. should be considered for the patients aged 70 and older, with moderate renal failure [creatinine clearance 30-50 mL/min], or with history of gastrointestinal haemorrhages, or those who are receiving P-gp inhibitors). The risks to the subjects are low after a single dose of 110 mg which is the dosage selected for the present study. Regardless of the low bleeding risk and the overall good tolerability of the available formulations of DE, subject's safety will be ensured by the monitoring of subjects for both expected and unexpected AEs clinically, verbally, and by laboratory monitoring. Based upon preclinical and clinical information, healthy subjects will not be exposed to undue risks from this trial.

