3. DESCRIPTION OF DESIGN AND TRIAL POPULATION

3.1 OVERALL TRIAL DESIGN AND PLAN

The trial will be performed as a randomised, single-dose, open-label, replicate design in, two-treatment, four-period, two-sequence crossover trial in healthy male subjects in order to compare the test treatment (T) to the reference treatment (R). The subjects will be randomly allocated to the two treatment sequences (T-R-R-T or R-T-T-R). The treatments will be single dose of 110 mg DE / formulation tablet in the fasting state (T) and single dose of 110 mg DE / formulation capsule in the fasting state (R). For details refer to [Section 4.1](#).

R(Reference treatment): DE commercial capsule formulation
 T(test treatment): DE tablet formulation

Figure 3.1: 1 Trial Design

There will be a washout period of at least 4 days between the treatments.

[figure not shown]

Figure 3.1: 2 Example of the timing of drug administration and washout period

An overview of all relevant trial activities is provided in the [Flow Chart](#). For visit schedule and details of trial procedures at selected visits, refer to [Sections 6.1](#) and [6.2](#), respectively.

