5.2.3 Assessment of safety laboratory parameters

For the assessment of laboratory parameters, blood and urine samples will be collected by the trial site at the time points indicated in the [Flow Chart](#) after the subjects have fasted for at least 10 h except for Visit 1. The subjects have fasted for at least 6 hours at Visit 1. Overnight fasting is not required at the discretion of the investigator or designee for retests.

The parameters that will be determined are listed in Tables 5.2.3: 1 and [5.2.3: 2](#). Reference ranges will be provided in the ISF, Section 10.

Manual differential white blood cell count should be performed if the investigator consider that further examination is necessary based on the results of automatic WBC differential regardless of the abnormality of the count.

Table 5.2.3: 1 Routine laboratory tests

Functional lab group	Test name
Haematology	Haematocrit
	Haemoglobin
	Red blood cell count (RBC)
	White blood cell count (WBC)
	Platelet count
Automatic WBC differential (relative)	Neutrophils, eosinophils, basophils, monocytes, lymphocytes
Manual differential WBC(if the investigator considers follow up is necessary)	Polymorphnuclear neutrophils (segs), band neutrophils (stabs), eosinophils, basophils, monocytes, lymphocytes
Coagulation	Activated partial thromboplastin time (aPTT)
	Prothrombin time (Quick's test and INR)
Enzymes	Aspartate transaminase (AST/GOT)
	Alanine transaminase (ALT/GPT)
	Alkaline phosphatase (AP)
	Gamma-glutamyl transferase (GGT)
Substrates	Plasma glucose
	Creatinine
	Total bilirubin
	Total protein
Electrolytes	Sodium
	Potassium

Table 5.2.3: 1 Routine laboratory tests (cont).

Functional lab group	Test name
Urinalysis ¹ (Stix)	Urine nitrite Urine protein Urine glucose Urine ketone Urobilinogen Urine bilirubin Urine erythrocytes Urine leukocytes Urine pH
Urine sediment ¹ (microscopic examination if erythrocytes, leukocytes nitrite or protein are abnormal in urine)	Only positive findings will be reported (for instance, the presence of sediment bacteria, casts in sediment, squamous epithelial cells, erythrocytes, leukocytes)
¹ Urinalysis/urine sediment only at screening and end of trial (EOT).	

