7.3.4 Safety analyses

Safety will be assessed for the endpoints listed in [Section 5.2.1](#). All treated subjects (that is, all subjects who received at least one dose of trial drug), will be included in the safety analysis. Safety analyses will be descriptive in nature and will be based on BI standards. No hypothesis testing is planned.

The analyses will be done by ‘treatment at onset’.

Treatments will be compared in a descriptive way. Tabulations of frequencies/proportions will be used for the evaluation of categorical (qualitative) data, and tabulations of descriptive statistics will be used to analyse continuous (quantitative) data.

Measurements (such as ECG, vital signs, or laboratory parameters) or AEs will be assigned to treatments (see [Section 4.1](#)) based on the actual treatment at the planned time of the measurement or on the recorded time of AE onset (concept of treatment emergent AEs).

Therefore, measurements planned or AEs recorded prior to first intake of trial medication will be assigned to 'screening', those between first trial medication intake until end of the residual effect period (see [5.2.2.2](#)) will be assigned to the treatment period. Events after the residual effect period but prior to next intake or end of trial examination will be summarized as 'post-treatment', those after the end of trial examination will be assigned to 'post-trial'. These assignments including the corresponding time intervals will be defined in detail in the TSAP.

Adverse events will be coded using the Medical Dictionary for Regulatory Activities. Frequency, severity and causal relationship of AEs will be tabulated by treatment, system organ class and preferred term. SAEs and other significant AEs (according to ICH E3) will be listed separately.

Laboratory data will be compared to their reference ranges. Values outside the reference range as well as values defined as clinically relevant will be highlighted in the listings. Additionally, differences from baseline will be evaluated.

Vital signs or other safety-relevant data observed at screening, baseline, during the course of the trial and at the end-of-trial evaluation will be assessed with regard to possible changes compared to findings before start of treatment.

Relevant ECG findings will be reported as AEs.

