7.8.2 Laboratory data

The analyses of laboratory data will be descriptive in nature by treatment sequence and will be based on BI standards (6).

Clinically relevant findings in laboratory data will be reported as AEs and will be analysed as part of AE analysis.

The last value on-treatment is defined as the last non-missing value observed during ‘on-treatment period’ (See section 7.8.1).

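### The single pre-period-1 baseline in SAP 6.7 leaves changes in periods 2 to 4 mixed with blood-sampling loss and time trend; add a period-specific baseline, summarised by formulation

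*SAP*

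**What the plan says.** SAP 6.7 sets the baseline for laboratory data and vital signs in the safety analysis; it is "defined as the last values before drug administration of period 1". Neither document defines a baseline for any later period.

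The values for one are collected. The Flow Chart block covering periods 1 to 4 has a safety laboratory sample at admission (-12:00) and another at 24:00. It has vital signs at -1:00, 2:00 and 24:00. Footnote 2 asks for "Safety laboratory to be taken and to be medically evaluated within 24 hours prior to administration of trial drug". Footnote 3 says of the -1:00 procedures that "the procedure can be acceptable to be performed and completed within 3 h prior to drug administration". Urinalysis is the exception: it is done only at screening and at the end of trial (protocol Table 5.2.3: 1).

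Protocol 7.3.4 assigns each measurement to the treatment actually given, plans a descriptive comparison of the treatments, and says of laboratory data: "Additionally, differences from baseline will be evaluated". SAP 7.8.2 summarises laboratory data by treatment sequence, and SAP 7.8.3 summarises vital signs by sequence and visit. Neither specifies a summary by formulation. SAP 7.8.2 adds: "The last value on-treatment is defined as the last non-missing value observed during" the on-treatment period of SAP 7.8.1. SAP section 4 declares no changes to the planned analysis.

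On sampling volume, protocol 2.3 states: "The total volume of blood withdrawn during the entire trial per subject will be around 285 mL".

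**The concern.** Each dose has its own before-and-after pair of blood laboratory values and vital signs, but for periods 2 to 4 the SAP does not use the before value as a baseline. A change reported in period 4 then starts from a value taken at least 12 days earlier (three intervals of at least 4 days) and spans three earlier treatment periods.

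This matters most for haemoglobin and haematocrit. Bleeding is the main drug risk named in protocol 2.3, and repeated sampling pushes both values in the same direction as bleeding would. Safety and tolerability are an additional objective (protocol 7.1.1), so a reader of the report will want to know what happened after a tablet and after a capsule. With one baseline and by-sequence tables, no specified summary of change isolates that.

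The last on-treatment value adds an ambiguity. Read across the whole trial, for a completer it is the 24 h sample of period 4. Its change from baseline then spans two tablet and two capsule doses.

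**Working it through.** The plan states no figure on this point, so there is none to reproduce. Three checks apply.

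**1. Residual drug from earlier doses.** Inputs: terminal half-life 8 to 9 h (protocol 1.2); washout of at least 4 days, or 96 h (protocol 3.1). The fraction left is 0.5^(96 / half-life).
- 8 h: 96/8 = 12.0 half-lives; 0.5^12.0 = 0.024%.
- 9 h: 96/9 = 10.7 half-lives; 0.5^10.7 = 0.062%.

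Adding all three earlier doses leaves both figures unchanged to this precision. Drug carry-over is below 0.1%.

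**2. Blood drawn before each dose.** Input: 285 mL for the whole trial (protocol 2.3). The volume per sample is not available, so I assume even draws over the four periods, with 85 to 100% of the total taken there and the rest at screening and end of trial.
- 100%: 285/4 = 71.25 mL per period, so 71, 142 and 214 mL before doses 2, 3 and 4.
- 85%: 0.85 × 285/4 = 60.6 mL per period, so 61, 121 and 182 mL.

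Further assumptions: blood volume 5 L, haemoglobin 15 g/dL, full dilution and no regeneration. Carried into the period-4 change:
- 182/5000 × 15 = 0.55 g/dL
- 214/5000 × 15 = 0.64 g/dL

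These are upper bounds. They scale directly with haemoglobin and inversely with blood volume. A pre-dose period-4 baseline removes this part. What remains is the sampling within the period, at most 60.6/5000 × 15 = 0.18 to 71.25/5000 × 15 = 0.21 g/dL.

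**3. Drift and the tablet-capsule contrast.** The sequences are TRRT and RTTR (protocol Table 4.1.4: 2). With a drift of d per period, a change from the period-1 baseline carries 0, d, 2d and 3d in periods 1 to 4. With a period-specific baseline this between-period component is 0 in each.

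| Data | Sequence | Mean drift, T | Mean drift, R |
|---|---|---|---|
| All four periods | TRRT | (0+3)/2 = 1.5d | (1+2)/2 = 1.5d |
| All four periods | RTTR | (1+2)/2 = 1.5d | (0+3)/2 = 1.5d |
| Stops after period 2 | TRRT | 0 | 1d |
| Stops after period 2 | RTTR | 1d | 0 |
| Stops after period 3 | TRRT | 0 | (1+2)/2 = 1.5d |
| Stops after period 3 | RTTR | (1+2)/2 = 1.5d | 0 |

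Linear drift cancels between formulations in complete data. Quadratic drift (0, 1, 4, 9) gives T 4.5 and R 2.5 in TRRT, and the reverse in RTTR. It is unequal within a sequence and cancels across two sequences of equal size. Within a subject who stops early, drift does not cancel.

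**The case against.** The case for leaving SAP 6.7 alone is substantial, and several stronger readings that a reader might infer do not stand.

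- **That the SAP contradicts the protocol.** It does not. For vital signs and other safety data, protocol 7.3.4 itself takes the state before treatment began as the reference, so a period-1 baseline is a legitimate implementation.
- **That later changes reflect earlier doses rather than the latest one.** The latest dose's effect is still in the change, and under 0.1% of earlier drug remains. Only lasting effects or unresolved events could carry over.
- **That the tablet-capsule comparison is biased.** In complete data drift cancels, and the SAP specifies no by-formulation table of change for the baseline to bias. The missing table is a gap of its own, which rewriting 6.7 alone would not close.
- **That later pre-dose values are discarded.** Nothing in the SAP drops them, and vital signs are tabulated at each planned visit. They are only not used as a baseline.
- **That haemoglobin falls by 0.86 g/dL in everyone and hides bleeding.** That figure is 285/5000 × 15, the whole trial's blood. It includes screening and end-of-trial samples, which cannot enter the period-4 change, and it assumes no regeneration. Clinically relevant laboratory changes also become adverse events, tabulated by treatment at onset, and that route does not depend on 6.7.
- **That the last on-treatment value must be a trial-wide one.** SAP 7.8.1 defines an on-treatment window after each intake, and SAP Table 6.1.1: 1 lists four separate treatment intervals, so a per-period reading is open. The laboratory displays also follow a sponsor standard not available here.

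Replacing the baseline would have its own cost. Period laboratory samples are at -12 h and 24 h, while the residual effect period is 3 days (protocol 5.2.2.2). A fall after 24 h would be absorbed into the next period's baseline, and cumulative loss would no longer show period by period. This argues for adding a baseline, not for swapping it.

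**Conclusion.** The point holds in a limited form. With the single baseline, by-period changes in periods 2 to 4 combine the latest formulation's effect with accumulated sampling loss and time trend, although pre-dose values that would separate them are collected before every dose. For haemoglobin the carried component in period 4 is at most about 0.55 to 0.64 g/dL, on the stated assumptions about sampling, blood volume, haemoglobin and regeneration.

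The distortion lies in absolute by-period changes and within subjects who stop early, not in the overall tablet-minus-capsule contrast in complete data. Early stopping need not be unrelated to safety, since protocol 3.3.4.1 removes subjects for clinically relevant bleeding. Separately, the by-sequence displays in SAP 7.8.2 and 7.8.3 fall short of the by-treatment description in protocol 7.3.4.

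The consequence is confined to descriptive safety with no hypothesis testing. The bioequivalence analysis is unaffected. The change is worth making because it is cheap and supplies a per-dose comparison that the SAP does not now specify.

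**What to change.** - **SAP 6.7:** keep the period-1 baseline for changes over the trial, including cumulative and end-of-trial change. Keep a single baseline for urinalysis. Add a second, period-specific baseline for blood laboratory tests and vital signs: the last value before that period's dose.
- **SAP 7.8.2:** state that the last on-treatment value is taken within each period.
- **SAP 7.8.2 and 7.8.3:** in addition to the by-sequence tables, summarise within-period changes by formulation (24 h for laboratory tests; 2 h and 24 h for vital signs).

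No new data are needed. The cost is SAP wording, some programming, a few extra tables, and clear labels so that the two baselines are not confused.
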